### 9.4.2 Secondary Endpoints

Secondary endpoints assess the effect of inhaled Ampion treatment compared to placebo on the clinical outcomes for participants with respiratory distress due to COVID-19. The secondary endpoints will be tested in a hierarchical manner in the order presented, and thus no adjustment to the alpha level is necessary:

Objective	Endpoint
Secondary	
Assess the effect of Ampion compared to placebo on safety	

Incidence of adverse events (AEs) and serious adverse events (SAEs) from baseline to Day 60.

Assess the effect of Ampion compared to placebo on clinical health	

Change in NEWS2 score from baseline through Day 5.

Change in NEWS2 score from baseline to hospital discharge.

Objective	Endpoint
Assess the effect of Ampion compared to placebo on hospital stay	
 
Hospital length of stay (LOS) from admission to discharge.
 

Assess the effect of Ampion compared to placebo on oxygen use	
 
Change from baseline in oxygen use, blood oxygen saturation, and oxygen flow rate from baseline through Day 5.
 

Assess the effect of Ampion compared to placebo on progression to respiratory failure	
 
Percentage of participants who progress to respiratory failure (i.e., need for mechanical ventilation, ECMO, non-invasive ventilation) by Day 28.
 

Assess the effect of Ampion compared to placebo on intensive care	
 
Percentage of participants who require Intensive Care Unit (ICU) admission by Day 28.
 
ICU-free days through Day 28.
 
ICU LOS from ICU admission to discharge.
 

Assess the effect of Ampion compared to placebo on all-cause mortality	
 
Percentage of participants with a successful outcome (life) or unsuccessful outcome (death) by Day 28.
 

The efficacy endpoints will be evaluated to estimate the treatment effect and use descriptive statistics including mean, standard deviation, percentages, minimum/maximum, and 95% confidence intervals. All endpoints will be tabulated and presented by treatment arm, cohort (moderate and severe), and timepoint. Where appropriate, data will be tabulated and presented cumulatively across cohorts and/or timepoints.

All binary outcomes are single incident percentages and thus the differences between the treatment groups will be tested using Fisher's exact test. The length of stay endpoints are also single incident endpoints the differences between the treatment groups will be tested using two sample t-test. All the other change from baseline variables are repeated assessments and will be analyzed utilizing a repeated measures analysis of variance.

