### 3.4 Blinding and Randomization

The treatment in this study will be blinded to the subjects, investigators, any individual conducting the study (e.g., nursing and pharmacy staff) and clinical study personnel. Participants will be assigned to treatment by a randomization schedule developed and maintained by an independent statistician.

Participants are randomized to active treatment or control, following an equal allocation to treatment arms, stratified by COVID-19 disease severity (severe or critical as defined in [Section 4.4](#)).

Study drug and placebo will be provided as blinded investigational product (IP) with appropriate labeling to link to the randomization code. Where required, safety personnel and/or investigator may be unblinded to a particular subject's treatment assignment to meet reporting requirements to Regulators.

A data management plan and statistical analysis plan will be approved by the sponsor prior to unblinding study data.

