Assess the effect of Ampion compared to placebo on intensive care	
Percentage of participants who require Intensive Care Unit (ICU) admission by Day 28.ICU-free days through Day 28.ICU LOS from ICU admission to discharge.

Assess the effect of Ampion compared to placebo on all-cause mortality	
 Percentage of participants with a successful outcome (life) or unsuccessful outcome (death) by Day 28.
--	--

The efficacy endpoints will be evaluated to estimate the treatment effect and use descriptive statistics including mean, standard deviation, percentages, minimum/maximum, and 95% confidence intervals. All endpoints will be tabulated and presented by treatment arm, cohort (moderate and severe), and timepoint. Where appropriate, data will be tabulated and presented cumulatively across cohorts and/or timepoints.

All binary outcomes are single incident percentages and thus the differences between the treatment groups will be tested using Fisher's exact test. The length of stay endpoints are also single incident endpoints the differences between the treatment groups will be tested using two sample t-test. All the other change from baseline variables are repeated assessments and will be analyzed utilizing a repeated measures analysis of variance.

Exploratory endpoints assess the effect of inhaled Ampion treatment compared to placebo on the clinical outcomes for participants with respiratory distress due to COVID-19 as follows:

Objective	Endpoint
Exploratory	
Assess the effect of Ampion compared to placebo on cytokine profile	
 Modulation of cytokine levels from baseline to Day 5.

The efficacy endpoints will be evaluated to estimate the treatment effect and use descriptive statistics including mean, standard deviation, percentages, minimum/maximum, and 95% confidence intervals. All endpoints will be tabulated and presented by treatment arm, cohort (moderate and severe), and timepoint. Where appropriate, data will be tabulated and presented cumulatively across cohorts and/or timepoints.

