4.1 Safety

Safety is measured by the incidence of adverse events (AEs) and serious adverse events (SAEs) from baseline to Day 60.

The hypotheses to be tested are:

$$H_0: \pi_A = \pi_S \text{ versus } H_A: \pi_A \neq \pi_S$$

Where π_A and π_S represent the proportion of patients who experience an AE or SAE for Ampion and Placebo during the first 60 days after randomization. The difference between Ampion and Placebo will be tested via an appropriate chi-square test or Fisher's exact test utilizing PROC FREQ with the EXACT option, if needed.

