4.5 Progression to Respiratory Failure

Progression to respiratory failure is measured as the percentage of participants who progress to respiratory failure (i.e., need for mechanical ventilation, ECMO, non-invasive ventilation) by Day

The hypotheses to be tested are:

$$H_0: \pi_A = \pi_S \text{ versus } H_A: \pi_A \neq \pi_S$$

Let π_A and π_S represent the proportion of patients who have respiratory failure for Ampion and control during the first 28 days after randomization. This difference will be tested utilizing the appropriate chi-square test or Fisher's exact test utilizing PROC FREQ with the EXACT option, if needed. Also, the median time to respiratory failure will be tested for difference between the two groups via the log-rank test. The log-rank test will be performed using PROC LIFETEST; and the estimation of the time-to-event distributions will be performed using the method of Kaplan and Meier.

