4.7 All-Cause Mortality

All-cause mortality is measured by the proportion of participants with a successful outcome (life) or unsuccessful outcome (death) by Day 28.

Let π_A and π_S represent the all-cause mortality rate of this outcome for Ampion and control during the study. Then it is desired to demonstrate that the mortality rate for Ampion is different than the corresponding rate for the control. Formally, this is presented as:

$H_0: \pi_A = \pi_S$ versus $H_A: \pi_A \neq \pi_S$

This will be tested utilizing the appropriate chi-square test or Fisher's exact test utilizing PROC FREQ with the EXACT option, if necessary. Also, the median time to death will be tested for difference between the two groups via the log-rank test. The test will be performed using PROC LIFETEST. The time to event distributions in each group will be estimated using the method of Kaplan and Meier.

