7. INTERIM ANALYSIS AND EARLY STOPPING GUIDELINES

7.1 Interim Analysis

The interim analysis is planned near the end of enrollment, after 150 patients, to test the protocol assumptions and estimates for clinical improvement, all-cause mortality rates and secondary endpoints as the available information and nature of the COVID-19 pandemic is rapidly evolving, which may impact estimates for both Ampion and control. The interim analysis will be used to determine if the sample size should remain at the planned 200 patients or increase based on the results of this analysis.

The interim analysis will be conducted on the primary and secondary endpoint data at an alpha level of 0.001, and thus the overall alpha level for the final test will be performed at $\alpha=0.047$ instead of the nominal value of $\alpha=0.05$. The sponsor also reserves the right to alter the final sample size if the assumptions of clinical improvement are not satisfied at this interim analysis.

The interim analysis uses the same hypothesis test described in the final analysis where μ_A and μ_S represent the mean changes in the ordinal scale for Ampion and control respectively. Then, it is desired to demonstrate that the mean change for Ampion is different than the corresponding mean change for the control, respectively. Formally, this is presented as:

$H_0: \mu_A = \mu_S$ versus $H_A: \mu_A \neq \mu_S$

The difference between Ampion and Placebo with respect to the change from baseline at Day 5 and Day 28 will be tested utilizing a Wilcoxon rank-sum test. To assess any potential time trends, an exploratory repeated measures analysis of variance will be performed with terms for treatment, time, and the interaction between the two.

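### No test of a binary secondary endpoint uses the severity strata, and the documents disagree on whether that test is Fisher's exact or chi-square

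*Protocol*

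**What the plan says.** **Test.** Protocol 9.4.2 says of the secondary endpoints: "All binary outcomes are single incident percentages and thus the differences between the treatment groups will be tested using Fisher's exact test". The general paragraph of SAP 4 has the same instruction ("thus the differences between the treatment groups will be tested using Fisher's exact test").

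The endpoint sections of the SAP differ. AE/SAE incidence (4.1) is to be "tested via an appropriate chi-square test or Fisher's exact test utilizing PROC FREQ with the EXACT option, if needed", and ICU admission (4.6) is worded alike. For respiratory failure (4.5): "This difference will be tested utilizing the appropriate chi-square test or Fisher's exact test utilizing PROC FREQ with the EXACT option, if needed". For Day 28 mortality (4.7): "This will be tested utilizing the appropriate chi-square test or Fisher's exact test utilizing PROC FREQ with the EXACT option, if necessary". No section says when the exact test becomes needed. Sections 4.5 and 4.7 add log-rank tests.

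**Strata.** Protocol 3.4 randomises "following an equal allocation to treatment arms, stratified by COVID-19 disease severity" (severe or critical). Protocol 9.3.1.5 and SAP 9.6 use severity only to split descriptive summaries. No binary or log-rank test is stratified by it or adjusted for it.

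**Level and direction.** SAP 7.1 states that "the final test will be performed at $\alpha=0.047$ instead of the nominal value of" 0.05. The hypotheses are two-sided; for mortality, "it is desired to demonstrate that the mortality rate for Ampion is different than the corresponding rate for the control".

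**The concern.** There are two separate weaknesses.

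1. The test is not fixed. One instruction requires Fisher's test throughout; the other prefers chi-square and leaves the switch to judgement. The reason given for Fisher's test, that each outcome is a single-incident percentage, does not call for an exact test. With two instructions and no rule, the p-value depends on a choice that could be made after the data are seen.

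2. The design factor is dropped. Patients in the critical stratum enter on high-flow oxygen, non-invasive ventilation or a ventilator, so severity may well predict death, ICU admission and respiratory failure. Stratified randomisation balances severity between arms. An unstratified test nevertheless counts the between-stratum variation as noise.

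What is at stake is power for mortality, respiratory failure, ICU admission and AE/SAE incidence, and p-values that do not depend on an analyst's choice.

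**Working it through.** **Inputs from the documents.** 100 per arm, 1:1; final two-sided level 0.047; Day 28 mortality 8% (Ampion) vs 26% (control), with 21% as the Phase I control rate; stated power at least 80% (Protocol 4.1 and 9.1, SAP 2.4).

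**Assumed, because the documents give no figures.** Critical share 30% or 50%; critical:severe outcome odds ratio (OR) 1, 3 or 6; equal arms within strata; and, for one scenario, respiratory failure at 20% vs 35%.

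**Step 1: the plan's own figure.** Power = Φ{[|p1−p2|√n − z√(2p̄(1−p̄))] / √(p1(1−p1)+p2(1−p2))}, with z = 1.986 at two-sided 0.047.
- 8% vs 26%: (1.8 − 1.986×0.531)/0.516 = 1.44, giving 92.6%. At level 0.05 it is 92.9%. Exact Fisher power is 90.9% at 0.047. The claim of at least 80% holds throughout.
- 8% vs 21%: (1.3 − 1.986×0.498)/0.489 = 0.64, giving 73.7%.

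**Step 2: Fisher against Pearson chi-square, exact enumeration over two binomials, no strata.**
- Fisher's true size at nominal 4.7%: 2.3% at a common rate of 8%, 2.5% at 10%, 3.1% at 17%, 3.2% at 21% and at 26%.
- Pearson's true size: 4.3% to 4.8% for rates from 5% to 30%.
- Power, Fisher vs Pearson: 90.9% vs 93.6% at 8% vs 26% (2.7 points); 68.1% vs 75.1% at 8% vs 21% (7.0 points). At assumed lower rates the gap grows: 56.7% vs 66.4% at 5% vs 15% (9.7 points).

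**Step 3: adding the strata.** Stratum rates q0 (severe) and q1 (critical) solve (1−s)q0 + s·q1 = p with q1/(1−q1) = OR·q0/(1−q0), where s is the critical share. The Cochran-Mantel-Haenszel (CMH) statistic, without continuity correction, is [Σ(a_h − n1h·m_h/N_h)]² / Σ[n1h·n2h·m_h(N_h−m_h)/(N_h²(N_h−1))], where stratum h has a_h events in the Ampion arm, m_h events in all, and arm sizes n1h and n2h with N_h = n1h + n2h.

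Simulated rejection rates with 30% critical (100,000 runs per row; 40,000 for the last row):

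| True rates | OR | Fisher | Chi-square | CMH |
|---|---|---|---|---|
| 26% both (null) | 1 | 3.2% | 4.8% | 4.7% |
| 26% both (null) | 6 | 2.0% | 3.2% | 4.6% |
| 8% vs 26% | 1 | 90.9% | 93.6% | 93.5% |
| 8% vs 26% | 3 | 91.4% | 93.9% | 94.4% |
| 8% vs 26% | 6 | 92.1% | 94.6% | 95.9% |
| 8% vs 21% | 1 | 68.1% | 75.1% | 74.8% |
| 8% vs 21% | 3 | 68.5% | 75.6% | 76.8% |
| 8% vs 21% | 6 | 68.9% | 76.1% | 79.2% |
| 20% vs 35% (assumed) | 6 | 60.7% | 67.4% | 72.6% |

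With 50% critical the mortality gains over chi-square are similar or slightly smaller (at 8% vs 21%: 1.1 points at OR 3, 2.2 at OR 6).

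**Step 4: hand check of the null row at OR 6.** The stratum rates are 15.1% and 51.5%. The within-stratum variance is 0.7×0.151×0.849 + 0.3×0.515×0.485 = 0.165, while the unstratified test uses 0.26×0.74 = 0.192. The true SD ratio is √(0.165/0.192) ≈ 0.925, so the effective cut-off is 1.986/0.925 = 2.15 and the size about 3.2%, as simulated.

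**Step 5: splitting the loss.** Fisher vs chi-square accounts for about 3 to 7 points at the documents' mortality rates. Ignoring severity (chi-square vs CMH) accounts for nothing at OR 1; 0.5 to 1.3 points at 8% vs 26% and 1.1 to 3.1 at 8% vs 21% for OR 3 to 6; and about 5 points at 20% vs 35% with OR 6. Over OR 3 to 6 and rates of 8% to 26%, the unstratified chi-square has a size of about 3.2% to 4.5%; CMH stays at 4.5% to 4.8%.

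**The case against.** The strongest reply is that the SAP's endpoint sections are the specific instructions and Protocol 9.1 sends the details to the SAP. On that reading chi-square is the default. At the planning rates about (8+26)/2 = 17 deaths per arm are expected under the null, so under the usual expected-count convention (an assumption; the SAP states none) mortality would get chi-square and Fisher's loss would not arise. This stands in part. A reader might infer that every binary endpoint, mortality included, will be tested by Fisher's test; the documents do not support that. But SAP 4 itself contains the Fisher sentence, nothing ranks the two instructions, and chi-square ignores severity too.

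Other tempting readings also go too far:

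- **That ignoring the strata causes the 2 to 3% size.** With non-prognostic strata Fisher's test is already at 2.3% to 3.3%. Most of the shortfall is its own conservatism.
- **That the loss is about 11 points.** A combined loss of that order needs an assumed OR near 6 or lower event rates than planned, and it is not a ceiling. At 8% vs 26% the total is about 3 to 4 points. The 20% vs 35% scenario is doubtful as well: some critical patients may meet the respiratory-failure definition at baseline, so its stratum rates are hard to interpret.
- **That the type I error rate is invalid.** A size below 0.047 still controls error.
- **That a conservative test blocks later steps in the hierarchy.** AE/SAE incidence comes first, and Protocol 2.3 reports adverse events as the same in both Phase I arms, so the sequence may stop there under any test. Mortality is last and blocks nothing.

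**Conclusion.** The point holds as an efficiency and specification problem on secondary endpoints. Two facts rest on the text alone: no binary or log-rank test uses the randomisation stratum, and the documents conflict on the binary test without a selection rule.

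The sizes rest on 100 per arm and level 0.047. If Fisher's test is used, true size is about 2 to 3% and the loss against chi-square is about 3 points at 8% vs 26% and 7 at 8% vs 21%. The further cost of ignoring severity is zero if severity is not prognostic and about 0.5 to 5 points for an OR of 3 to 6; those ORs and the stratum shares are assumptions. Error is not inflated, and the plan's power statement at 8% vs 26% survives. The lower control rates deserve some weight, because Protocol 3.2.1 itself says that progression to ventilation or death has fallen. The change should be made, but the trial's validity does not depend on it.

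**What to change.** In Protocol 9.4.2 and SAP 4, 4.1, 4.5, 4.6 and 4.7, replace the competing sentences with one test for all binary secondary endpoints, fixed before any unblinded look, including the interim:

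- Cochran-Mantel-Haenszel test stratified by randomised severity (severe, critical), two-sided, without continuity correction.
- Exact stratified version under a stated rule, for example when the expected count of events (or of non-events), summed over strata, is below 5 in either arm.
- Mantel-Haenszel risk difference with its confidence interval.
- Log-rank tests for death and respiratory failure stratified by severity.

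The cost is wording plus about one line each in PROC FREQ and PROC LIFETEST, with no new data or patients. The statistical downside is small: if severity is not prognostic, CMH gives up under half a point against chi-square at the documents' mortality rates (75.1% vs 74.8% at 8% vs 21%), and about half a point at 5% vs 15% (66.7% vs 66.1%).

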#### 9.4.3 Exploratory Endpoints

Exploratory endpoints assess the effect of inhaled Ampion treatment compared to placebo on the clinical outcomes for participants with respiratory distress due to COVID-19 as follows:

Objective	Endpoint
Exploratory	
Assess the effect of Ampion compared to placebo cytokine profile	
 
Modulation of cytokine levels from baseline to Day 5.
 

The efficacy endpoints will be evaluated to estimate the treatment effect and use descriptive statistics including mean, standard deviation, percentages, minimum/maximum, and 95% confidence intervals. All endpoints will be tabulated and presented by treatment arm, cohort (moderate and severe), and timepoint. Where appropriate, data will be tabulated and presented cumulatively across cohorts and/or timepoints.

#### 9.5 Missing and Spurious Data

All data collected under this study protocol will be included in the assessment of patient safety. Missing or incomplete AE data will assume greatest relationship to study drug and/or severity.

For the ordinal score effectiveness endpoint analysis of clinical outcomes at Day 5 and Day 28, a sensitivity analysis will be performed for all participants that have been discharged from the hospital, cannot be reached via telephone contact, and their death status is not known. The sensitivity analysis will be performed where missing ordinal scale status at Day 5 and Day 28 will be replaced as having died (Ordinal score 8).

## **10 REGULATORY, ETHICAL AND LEGAL OBLIGATIONS**

### **10.1 Declaration of Helsinki**

The Principal Investigator will ensure that this Study is conducted in accordance with the most recent revision of the Declaration of Helsinki.

### **10.2 Good Clinical Practice**

The Study will be conducted according to the study protocol and to Standard Operating Procedures (SOPs) that meet the guidelines provided by the International Conference on Harmonization (ICH) for Good Clinical Practice in clinical studies.

### **10.3 Institutional Review Boards/Ethics Committees**

Before implementing this study, the protocol, the proposed patient informed consent forms and other information for the patients must be reviewed by a properly constituted committee or committees responsible for approving clinical studies. The IRB/IEC written signed approval letter/form must contain approval of the designated investigator, the protocol (identifying protocol title, date, and version number), and of the patient informed consent form (date, version).

Any change or addition to the protocol can only be made in a written protocol amendment that must be approved by the Sponsor, the IRB/IEC, and the Health Authorities.

### **10.4 Regulatory Authority Approval**

Before this study is implemented, the protocol must be approved by the relevant regulatory authority.

### **10.5 Informed Consent**

The investigator must fully inform the patient or patient's legally authorized representative of all pertinent aspects of the trial including the written information approved/favorably assessed by the IRB/IEC.

Prior to the start of the pre-study examination, the written informed consent form must be signed and personally dated by the patient, or the patient's legally authorized representative, and by the physician who conducted the informed consent discussion. One copy of the written information and signed consent form must be given to each patient or the patient's legally authorized representative, and one (1) copy must be retained in the investigator's study records.

### **10.6 Patient Confidentiality and Disclosure**

Data on patients collected on eCRFs during the trial will be documented in an anonymous fashion and the patient will only be identified by the subject unique identification number. If, as an exception, it is necessary for safety or regulatory reasons to identify the patient, all parties are bound to keep this information confidential.

The investigator will guarantee that all persons involved will respect the confidentiality of any information concerning the trial patients. All parties involved in the study will maintain strict confidentiality to assure that neither the person nor the family privacy of a patient participating in the trial is violated. Likewise, the appropriate measures shall be taken to prevent access of non-authorized persons to the trial data.

## **10.7 Collection, Monitoring and Auditing Study Documentation, and Data Storage**

### **10.7.1 Collection of Data and Monitoring Procedures**

This study will use a 21 CFR Part 11 compliant electronic data capture system (EDC). An electronic case report form (eCRF) is used for data recording. All data requested on the eCRF must be entered and all missing data must be accounted for.

The data will be checked for completeness and correctness as it is entered by the real-time online checks applied by the EDC system. Off-line checks will also be run to perform any additional data review required. Discrepancy reports will be generated accordingly and transferred to the study center for resolution by the investigator or his/her designee.

Accurate and reliable data collection will be assured by verification and cross-check of the eCRF against the investigator's records by the study monitor (source document verification), and the maintenance of a study drug-dispensing log by the investigator.

Before study initiation, at a site initiation visit or at an investigator's meeting, a Sponsor representative will review the protocol and case report forms with the investigators and their staff. During the study a monitor will visit the site regularly to check the completeness of patient records, the accuracy of entries on the case report forms, the adherence to the protocol and to Good Clinical Practice, the progress of enrollment. The monitor will ensure during on-site visits that study medication is being stored, dispensed and accounted for according to specifications. Key trial personnel must be available to assist the monitors during these visits.

The investigator must give the monitor access to relevant hospital or clinical records, to confirm their consistency with the case report form entries. No information in these records about the identity of the patients will leave the study center. Monitoring standards require full verification for the presence of informed consent, adherence to the inclusion/exclusion criteria, documentation of SAEs and the recording of primary efficacy and safety variables. Additional checks of the consistency of the source data with the eCRFs are performed according to the study-specific monitoring plan.

